All interventional cardiology methods for treatment of coronary artery disease.

RESTENOTIC LESION

Lesion in a vessel segment that has undergone prior percutaneous treatment with or without a stent placement.

REFERENCE VESSEL DIAMETER (RVD)

Average of normal segments within 10 mm proximal and distal to target lesion from two orthogonal views using quantitative coronary angiography.

STENT THROMBOSIS – ACADEMIC RESEARCH CONSORTIUM-2 (ARC-2) DEFINITION¹

Classification	Criteria
Definite stent thrombosis	Angiographic confirmation of stent thrombosis*
	The presence of a thrombus† that originates in the stent or in the segment 5 mm proximal or distal to the stent or in a side branch originating from the stented segment and the presence of at least 1 of the following criteria:
	Acute onset of ischemic symptoms at rest
	New electrocardiographic changes suggestive of acute ischemia
	Typical rise and fall in cardiac biomarkers (refer to definition of spontaneous myocardial infarction)
	Or
	Pathological confirmation of stent thrombosis
	Evidence of recent thrombus within the stent determined at autopsy
Examination of tissue retrieved following thrombectomy (visual/histology)	
Probable stent thrombosis	Regardless of the time after the index procedure, any myocardial infarction that is related to documented acute ischemia in the territory of the implanted stent/scaffold without angiographic confirmation of stent/ scaffold thrombosis and in the absence of any other obvious cause.‡
Silent stent occlusion	The incidental angiographic documentation of stent occlusion in the absence of clinical signs or symptoms is not considered stent thrombosis.
Timing of ST (duration after stent implantation)	
Acute	0§–24 h
Subacute	>24 h–30 d
Late	>30 d–1 y
Very Late	>1 y

Early stent thrombosis is 0 to 30 days (acute plus subacute stent thrombosis).

*Definite stent thrombosis is considered to have occurred by either angiographic or pathological confirmation.

†Occlusive thrombus: Thrombolysis in Myocardial Infarction grade 0 or 1 flow within or proximal to a stent/scaffold segment. Nonocclusive thrombus: intracoronary thrombus is defined as a (spherical, ovoid, or irregular) noncalcified filling defect or lucency surrounded by contrast material (on 3 sides or within a coronary stenosis) seen in multiple projections, persistence of contrast material within the lumen, or visible embolization of intraluminal material downstream.

‡When the stented segment is in the left circumflex coronary artery or in the presence of preexisting electrocardiographic abnormalities (e.g., left bundle branch block, paced rhythms), definitive evidence of localization may be absent and Clinical Events Committee adjudication is based on review of all available evidence).

§Defined as the moment the patient is undraped and taken off the catheterization table.

TARGET LESION FAILURE (TLF)

Cardiac death, target vessel myocardial infarction (Q-wave or non-Q-wave), or clinically-driven target lesion revascularization.

TARGET LESION REVASCULARIZATION (TLR)

Repeat percutaneous intervention of the target lesion or bypass surgery of the target vessel performed for restenosis or other complication of target the lesion.

The target lesion is defined as the treated segment including the 5 mm margin proximal and distal to the stent.

See also *Clinically Driven Target Lesion Revascularization*.

TARGET VESSEL FAILURE (TVF)

Composite endpoint comprised of cardiac death, target vessel myocardial infarction or clinically-driven target vessel revascularization.

Target vessel failure will be reported when any of the following events occur:

- Recurrent MI occurs in territory not clearly attributed to a vessel other than target vessel.
- Cardiac death not clearly due to a non-target vessel endpoint.
- Target vessel revascularization is determined.

TARGET VESSEL MYOCARDIAL INFARCTION (MI)

Myocardial infarction that occurs in a territory that cannot be clearly attributed to a vessel other than the target vessel.

TARGET VESSEL REVASCULARIZATION (TVR)

Repeat percutaneous intervention or surgical bypass of any segment of the target vessel.

Target vessel is defined as the entire major coronary vessel proximal and distal to target lesion, including upstream and downstream branches and the target lesion itself.

See also *Clinically Driven Target Vessel Revascularization*.

THROMBOLYSIS IN MYOCARDIAL INFARCTION (TIMI) CLASSIFICATION²⁷

System developed during Thrombolysis in Myocardial Infarction (TIMI) trials for grading severity of stenosis and extent of blood flow through coronary arteries.

TIMI 0: No perfusion.

TIMI 1: Penetration with minimal perfusion. Contrast fails to opacify entire bed distal to stenosis for duration of cine run.

TIMI 2: Partial perfusion. Contrast opacifies entire coronary bed distal to stenosis. However, rate of entry and/or clearance is slower in coronary bed distal to obstruction than in comparable areas not perfused by dilated vessel.

TIMI 3: Complete perfusion. Filling and clearance of contrast equally rapid in the coronary bed distal to stenosis as in other coronary beds.

TOTAL OCCLUSION

Lesion with no flow (TIMI 0). Total occlusions are usually classified as persisting less than or more than 3 months (chronic total occlusion).

18 Study Milestones / Timeline

The timeline of the BIOFLOW-VII study is dependent on the date of FDA approval of the study protocol, the ability to recruit a sufficient number of interested sites, and the ability to enroll subjects.

Progress reports will be submitted every 6 months during the first 2 years of the study and annually thereafter, unless otherwise specified by FDA.

Milestone	Window	Estimated Date
FDA Approval of Orsiro (P170030)	---	February 22, 2019
FDA approval of PAS protocol	Approval	November 2019
First IRB approval and first site opened to enrollment	Approval + 3 months	February 2020
First subject enrolled	Approval + 3 months	February 2020
Enrollment of 10 subjects	Approval + 5 months	April 2020
Enrollment of 100 subjects	Approval + 9 months	August 2020
All sites opened	Approval + 18 months	May 2021
Enrollment completion	Approval + 18 months	May 2021
Final 12-month follow-up visit (Primary Endpoint)	Enrollment Completion + 12 months + Visit Window (Approval + 31 months)	June 2022
Final 5-year follow-up visit (Study Completion)	Enrollment Completion + 60 months + Visit Window (Approval + 81 months)	July 2026
Final report submitted to FDA	Study Completion + 6 months (Approval + 87 months)	January 2027

19 References

- ¹ Garcia-Garcia H, McFadden EP, Farb A, et al. Standardized End Point Definitions for Coronary Intervention Trials The Academic Research Consortium-2 Consensus Document. *Circulation*. 2018;137:2635-2650.
- ² Doros G, Massaro JM, Kandzari DE et al. Rationale of a novel study design for the BIOFLOW V study, a prospective, randomized multicenter study to assess the safety and efficacy of the Orsiro sirolimus-eluting coronary stent system using a Bayesian approach. *Am Heart J*. 2017 Nov 1;193:35-45.

1.1 Study Purpose

The objective of this post-approval study is to confirm that the clinical performance of the Orsiro[®] Sirolimus Eluting Coronary Stent (hereinafter referred to as Orsiro) in a real-world setting is similar to the clinical performance observed for Orsiro in the pivotal BIOFLOW-V study.

1.2 Study Design

BIOFLOW-VII is a prospective, multi-center, single-arm study. The study will enroll 556 subjects to achieve 500 evaluable subjects at up to 50 sites in the United States (US). Clinical outcomes will be collected and reported through 5 years post-index procedure. The design includes comparison against a performance goal based on the BIOFLOW-V trial Orsiro target lesion failure (TLF) rate, taking into consideration TLF rates from other US market-released drug-eluting stents (DES).

1.3 Primary Endpoint

The primary endpoint of the study is Target Lesion Failure (TLF) rate at 1-year post-index procedure. TLF is defined as a composite of cardiac death, protocol-defined target vessel myocardial infarction (MI), or clinically-driven target lesion revascularization (TLR).

The TLF rate will be derived from events adjudicated by the CEC to be a cardiac death, protocol-defined Q-wave or non-Q-wave target vessel myocardial infarction, or a clinically-driven target lesion revascularization according to the CEC Charter definitions.

1.4 Secondary Endpoints

The following secondary endpoints will be evaluated prior to discharge, at 1 month, 1 year, and annually thereafter through 5 years follow-up (unless otherwise specified).

- 1. All-cause death.
- 2. Protocol-defined MI.
- 3. Cardiac death or Protocol-defined MI.
- 4. Major Adverse Cardiovascular Events (MACE) and individual MACE components (MACE: composite of allcause death, Q-wave or non–Q-wave MI, and clinically-driven TLR).
- 5. TLF (evaluated at discharge, 1 month, 2, 3, 4, and 5 years) and individual TLF components (TLF: composite of cardiac death, target vessel Q-wave or non–Q-wave MI, and clinically-driven TLR).
- 6. Target vessel failure (TVF) and individual TVF components [TVF: composite of cardiac death, target vessel Q-wave or non–Q-wave MI, and clinically-driven target vessel revascularization (TVR)].
- 7. Stent thrombosis (definite, definite/probable, probable) according to Academic Research Consortium (ARC)-2¹ criteria for acute, subacute, late, very late, and cumulative stent thrombosis.

The secondary endpoints include the following measures assessed at the time of the index procedure:

Version 1.0	05-18-2022	Confidential
	Do not copy	or distribute without sponsor approval

1. Device success, defined as attainment of < 30% residual stenosis of the target lesion (based on operator visual estimate) using the Orsiro study stent only.

Note: Post-dilatation is allowed to achieve device success.

- 2. Lesion success, defined as attainment of < 30% residual stenosis of the target lesion (based on operator visual estimate) using any percutaneous method.
- 3. Procedure success, defined as attainment of < 30% residual stenosis of the target lesion (based on operator visual estimate) using the Orsiro study stent only without occurrence of in-hospital MACE.

2 Planned Analyses

The planned analyses described below will be performed when the data required to complete the analysis is available. Generally, the results of completed analyses will be provided within the next scheduled clinical progress report, unless BIOTRONIK identifies that a separate communication is required. If the planned analysis time point has not yet been met, progress toward the analysis and current available data will be presented using descriptive statistics within the clinical progress report.

2.1 Analysis Definitions

Descriptive statistics will be used to present and summarize the data collected in the clinical study. Frequency distributions and cross tabulations will be presented for discrete variables. Means, standard errors, and ranges will be presented for continuous variables. Proportions will be calculated using known non-missing values.

Unless otherwise indicated, all statistical tests and/or confidence intervals will be performed at α = 0.05 (2-sided).

2.2 Statistical Analysis Sets

2.2.1. Intention to Treat (ITT) Analysis Population

The ITT population is defined as all enrolled subjects who received at least one Orsiro stent and were not considered a screen failure. This is the primary analysis population and data presented within the clinical progress report will be the ITT population unless otherwise specified.

2.2.2. Per-Protocol (PP) Analysis Population

The PP population is defined as all ITT subjects who have no major protocol eligibility violations that could impact the primary endpoint. Subjects that provided written informed consent but did not meet key inclusion/exclusion criteria were exited from the study as screen failures per Table 2 of the protocol. If any key criteria outlined in Table 2 were identified after the subject had been followed through the 1-month follow-up visit, the subject was not exited as a screen failure but will be excluded from the Per Protocol population.

The Per Protocol population will also exclude subjects that did not meet additional protocol eligibility criteria that were deemed to potentially affect the primary endpoint such as 'Presence of an untreated clinically significant stenosis post-procedure whether treatment is planned or not' or 'Subject is receiving chronic anticoagulation (e.g. coumadin, dabigatran, apixaban, rivaroxaban or any other agent)'.

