2.3 Subject Status

The definitions in **Table 2** define subject statuses throughout the study. Screen failure criteria are defined to target enrollment of a 100% on-label population.

Table 2: Subject Status Definitions

Subject Status	Definition
Enrolled	Subject who successfully meets all inclusion/exclusion criteria and provides written informed consent.
Pre-Screen failure	Subject in whom an Orsiro stent is deployed (or in whom an Orsiro stent implantation is attempted) and informed consent is not obtained due to subject not meeting inclusion/exclusion criteria or subject is not willing to participate in the study.

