4.3.2 Analysis Population Definition(s)

Table 6 provides definitions of the study analysis populations.

Table 6: Study Analysis Populations

Analysis Population	Definition
Intent-to-Treat (ITT)	The ITT population is defined as all enrolled subjects who received at least one Orsiro stent and were not considered a screen failure.
Per-Protocol (PP)	The PP population is defined as all ITT subjects who have no major protocol eligibility violations that could impact the primary endpoint. Criteria defining the PP population will be pre-specified prior to any PP analyses being performed.

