Cardiac Death: Death due to immediate cardiac cause (e.g., myocardial infarction, low-output failure, fatal arrhythmia). Unwitnessed death and death of unknown cause will be classified as cardiac death. This includes all procedure-related deaths, including those related to concomitant treatment.

Vascular Death: Death due to cerebrovascular disease, pulmonary embolism, ruptured aortic aneurysm, dissecting aneurysm or other vascular cause.

Non-Cardiovascular Death: Death not covered by the above definitions, including death due to infection, sepsis, pulmonary causes, accident, suicide or trauma.

ENROLLED SUBJECT

Subject who meets all clinical and angiographic eligibility criteria and has provided informed consent by properly signing an informed consent form.

Enrolled subjects will be followed in accordance with the protocol requirements.

EVALUABLE SUBJECT

Enrolled subject who meets all inclusion/exclusion criteria. Subject is part of the Intent-to-Treat analysis population.

INTRACORONARY THROMBUS

Presence of a filling defect within lumen, surrounded by contrast material seen in multiple projections in absence of calcium within the filling defect, or persistence of contrast material within lumen, or a visible embolization of intraluminal material downstream.

MAJOR ADVERSE CARDIAC EVENTS (MACE)

All-cause death, myocardial infarction (Q-wave or non-Q-wave), any clinically-driven target lesion revascularization.

MINIMAL LUMINAL DIAMETER

Average of two orthogonal views (when possible) of the narrowest point within the area of assessment – in lesion, in stent or in segment. Visually estimated during angiography by the investigator and measured during QCA by the angiographic core laboratory.

MYOCARDIAL INFARCTION – PROTOCOL DEFINITION

Different criteria for spontaneous and peri-procedural MI will be utilized for the primary adjudication for endpoints for MI.

Peri-procedural < 48 hours post PCI Society for Cardiovascular Angiography and Interventions (SCAI) definition⁴

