2.3 Primary Endpoint Analysis

The purpose of the primary endpoint is to evaluate the rate of TLF of the Orsiro stent at 1 year compared to a performance goal of 6.9%.

 $H_{0}:$ The TLF rate of the Orsiro stent at 1 year is greater than or equal to a performance goal of 6.9%

Rate ≥ 6.9%

 $H_a:$ The TLF rate of the Orsiro stent at 1 year is less than a performance goal of 6.9%

Rate < 6.9%

Version 1.0 05-18-2022

Confidential

Page 4 of 11

Do not copy or distribute without sponsor approval

A rejection of the null hypothesis (H_{\circ}) would demonstrate that the primary endpoint is met.

TLF is defined as a composite of cardiac death, target vessel-MI or clinically-driven TLR. Target vessel MI will utilize the SCAI definition² for peri-procedural MI and the BIOFLOW-V protocol definition³ for spontaneous MI.

The primary analysis of the primary endpoint of the TLF rate of the Orsiro stent at 1 year will be in the intent-totreat (ITT) population. The primary endpoint will be tested against a performance goal of 6.9% using a one-sided, exact test for one proportion with a Type I error level of 0.025. An additional (one-sided) supporting analysis will be performed in the PP population. A Kaplan-Meier survival analysis (time-to-event) for the primary endpoint outcome will be performed for the ITT and PP populations.

For each analysis population, subjects who have sufficient follow-up data (at least 330 days of follow-up), based on all available collected dates, or experienced the primary endpoint will be included in the primary endpoint analysis.

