2.12 Adverse Event Analysis

Adverse events collected in the BIOFLOW-VII data will be summarized using descriptive statistics that describe the percentage of subjects experiencing an adverse event and rate of adverse event as events per subject-year. The total number of enrolled ITT subjects and cumulative duration of follow-up completed for the enrolled subjects as of the date of the report will be utilized to calculate the descriptive statistics. AE rates will be presented by System Organ Class and Sub-category for the following:

- Site-reported AEs
- Site-reported device/procedure-related AEs
- Site-reported SAEs
- Site-reported device/procedure-related SAEs

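### A TLF event before a screen-failure exit enters no planned endpoint analysis, and a 1-month rule found only in the SAP decides which subjects breaching key criteria stay in ITT

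*SAP*

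**What the plan says.** **Order of events.** Under Protocol 3.1.3 and 3.2.3, consent is given within 24 hours after the index procedure, so a consented subject normally already has the device. Eligibility is to be confirmed before consent.

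**Screen failure in the protocol.** Table 2 (Section 2.3) and Section 3.4.6 say that a consented subject who fails key criteria is a screen failure and is exited. No time limit is given. The stated reason is: "Screen failure criteria are defined to target enrollment of a 100% on-label population".

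**Analysis sets.** Protocol 4.3.2: "The ITT population is defined as all enrolled subjects who received at least one Orsiro stent and were not considered a screen failure". SAP 2.2.1 repeats this definition, and PP is drawn from ITT in both documents.

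**What uses those sets.** The primary test is in ITT with PP as support. SAP 2.3 adds: "A Kaplan-Meier survival analysis (time-to-event) for the primary endpoint outcome will be performed for the ITT and PP populations". Secondary endpoints use ITT and PP (SAP 2.6). Adverse-event rates are based on "The total number of enrolled ITT subjects and cumulative duration of follow-up completed for the enrolled subjects" (SAP 2.12). The sensitivity analyses in SAP 2.5 and 2.14 add no screen failures back.

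**The SAP rule.** SAP 2.2.2 says that if a Table 2 breach was "identified after the subject had been followed through the 1-month follow-up visit, the subject was not exited as a screen failure"; that subject is instead excluded from PP.

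**The concern.** In most trials a screen failure has not been treated. Here the screen failures at issue have received the stent, so removing them is an exclusion after treatment. An MI in the first 48 hours, an early stent thrombosis leading to revascularization, or an early cardiac death would be a TLF event. If the subject is then exited as a screen failure, the event is in no planned endpoint analysis.

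The SAP rule also makes ITT membership depend on when a breach is noticed. The same key-criterion breach takes a subject out of ITT if found before the 1-month visit is completed, but only out of PP if found later. Breaches of other criteria stay in ITT whenever they are found. An event may itself prompt a closer look at the records, and nothing requires the eligibility decision to be made without knowledge of outcome.

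The primary conclusion is pass or fail against 6.9%. Near the limit, one or two such events could decide it, and no planned analysis would show that they had.

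**Working it through.** **Inputs from the documents** (Protocol 4.2.1 and 4.3.3; SAP 2.3 and 2.4): performance goal 6.9%; assumed true rate 4.0%; one-sided exact test at 0.025; power 80%; 495 evaluable subjects, raised to 500; 10% attrition. The BIOFLOW-V Orsiro rate under the SCAI definition is 2.6%.

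**1. The plan's own figure.** The critical count c is the largest x with P(X ≤ x | n, 0.069) ≤ 0.025, and power is P(X ≤ c | n, 0.04). At n = 494, c = 22 and power is 74.2%. At n = 495, c = 23, the actual level is 0.0245 and power is 80.5%. So 495 reproduces, and 500/0.9 = 555.6 gives 556.

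**2. The limit at n = 500.** 23/500 gives p = 0.0214 (pass). 24/500 gives p = 0.0338 (fail).

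**3. Restoring one event, with event-free exits also counted.** Start from 23/500 and add m exited subjects, one of whom had a TLF event. The documents give no number of exits, so m is assumed.

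| m | Events/n | Exact p | Result |
|---|---|---|---|
| 5 | 24/505 | 0.0297 | fail |
| 10 | 24/510 | 0.0261 | fail |
| 20 | 24/520 | 0.0200 | pass |

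**4. The same with censoring.** A simple proportion credits an exited subject with a full event-free year. Kaplan-Meier does not. Its log-log upper 97.5% bound is 1 − S^exp(1.96·se), with se = √(Σ d/[n(n−d)]) / |ln S|. Assumptions: 500 ITT subjects fully followed; 12 or 4 of the ITT events on day 1 and the rest on days 40–350; exits censored on day 15; restored events on day 1.

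- 23 ITT events, none restored: 6.84%.
- One restored among 5, 10 or 20 exits: 7.03–7.05%, 7.00–7.04% and 6.93–7.01%, all above 6.9%.
- 22 ITT events, one restored among 5 or 10: 6.76–6.82%, still below.

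**5. How often this would matter.** The quantity is the chance that ITT passes (at most 23/500) and the restored bound reaches 6.9%, for event risk r before exit.

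| m | r | True rate 4.0% | True rate 2.6% |
|---|---|---|---|
| 5 | 1% | 0.3% | 0.02% |
| 10 | 2% | 1.4% | 0.07% |
| 20 | 2% | 2.8% | 0.16% |

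Hand check for the middle row at 4.0%: P(X = 23) = 0.068, and P(at least one event in 10) = 1 − 0.98^10 = 0.183. Their product is 0.0124. The case of 22 ITT events with two or more restored adds about 0.078 × 0.016 = 0.0013. The sum is about 1.4%.

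**The case against.** **The exclusion is a declared choice.** Both documents use the same ITT definition, for a stated on-label aim. A set that includes off-label subjects answers a different question from the one 6.9% was set for. This stands, and it is why the primary analysis should not change.

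**Exits may be few.** Eligibility is to be settled before consent, and the SAP rule limits late removals. Both points stand. But Table 2 provides for failures after consent, and SAP 2.2.2 for breaches found beyond a month, so the sponsor expects some.

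**Protocol 3.4 says data up to exit will be used.** The situations it lists are death, withdrawal of consent and an investigator's safety decision. Screen failure is not among them, and the ITT definition does not carry the statement through. It does bear on deaths: it suggests that a subject who exits by death is kept. The SAP does not say how a subject who dies before the 1-month visit and is then found ineligible is classed.

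**Other outputs may reveal something.** Noncompliance is reported to FDA (Protocol 8), the SAP plans by-subject listings of it (2.14), and the CEC rules on all deaths (Protocol 10.2). These may show a breach or a death, but they do not put a TLF event into an endpoint estimate.

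**A stronger reading to avoid.** Table 2 defines an enrolled subject as "Subject who successfully meets all inclusion/exclusion criteria and provides written informed consent", and the Glossary (Section 17) defines an evaluable subject as "Enrolled subject who meets all inclusion/exclusion criteria. Subject is part of the Intent-to-Treat analysis population". A reader might infer that the protocol bars every late-found ineligible subject from ITT and that the SAP contradicts it. The documents do not support this. Protocol 4.3.2 defines PP as ITT subjects without major eligibility violations, and Section 8.1 lists eligibility violations, so some ineligible subjects are expected in ITT.

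**Conclusion.** The gap is real and follows from the documents' own definitions: a TLF event in a consented, stented subject before a screen-failure exit is in no planned endpoint analysis. For Table 2 criteria only, the date on which a breach is found decides ITT membership, under a rule that the protocol does not state.

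It is an unexamined sensitivity. A reader might infer that events were removed selectively or that the primary result is biased. Nothing in the documents shows that, and they give no count of exits or of events before exit.

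The effect is confined to results at or next to 23/500. Even there, one restored event does not always reverse the exact test: with 20 exits counted, 24/520 passes. Under the assumptions of 5–20 exits and 1–2% risk before exit, the chance of reversing a pass is about 0.3–2.8% at a true rate of 4.0% and 0.02–0.16% at 2.6%. Larger figures need a risk before exit above the 4.0% assumed for the whole year, and I do not rely on them. This is a cheap improvement worth making, not a flaw in the primary analysis.

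**What to change.** 1. Keep the primary ITT analysis. Add to SAP 2.3/2.5 a supportive sensitivity analysis of 1-year TLF in all consented subjects who received at least one Orsiro stent, including those exited as screen failures. Use Kaplan-Meier with censoring at exit or last contact, and report the estimate and its upper 97.5% bound beside 6.9%. Do not apply the 330-day-or-event rule to it: early-exited subjects would then be admitted only if they had an event.
2. List screen failures by Table 2 reason, day the breach was identified, exit day, and known TLF events and SAEs before exit.
3. Reconcile the 1-month rule between protocol and SAP. State how a death before the 1-month visit is classed, consistently with Protocol 3.4. Make the remaining eligibility and PP decisions without knowledge of outcome.

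**Cost:** one analysis, one listing and a short text change. Little new data is needed: events from the start of the index procedure are collected (Protocol 5.2), and reported potential endpoint events go to the CEC (10.2). **Limits:** exited subjects lie outside the on-label population, have short follow-up, and may lack the minimum data that the CEC requires, so the analysis can only be supportive.
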